The effectiveness of influenza vaccines in high-risk groups is understudied. These populations are at increased risk of severe influenza-related complications, and at the same time their immune systems produce weaker responses to vaccination. A recent study on the effectiveness of 2023 Southern Hemisphere influenza vaccines across eight countries (Argentina, Australia, Brazil, Chile, New Zealand, Paraguay, Thailand, and Uruguay) estimated a pooled vaccine effectiveness of 56.6% (46.2-67.1) against SARI hospitalization among children and adults aged 5-64 years with underlying health conditions. Country-specific estimates varied, ranging from 59.3% (45.9-69.4) in Australia to 28.2% (-44.9 to 64.4) in New Zealand.(6) In immunosuppressed cancer patients, vaccination was associated with lower mortality and reduced risk of influenza-related complications (7), and in RCTs including COPD patients, vaccination was associated with fewer exacerbations (8). In a prospective US evaluation during 2012-16, VE against any influenza was lower among patients with high-risk conditions (41%) than those without (48%; P-for-interaction = 0.02) (9).

VE will vary across different influenza virus subtypes (10,11). A meta-analysis reported pooled VE estimates among older adults of 24% for H3N2, 63% for type B and 62% for H1N1pdm09 (10). In a more recent multi-site evaluation, VE estimates ranged from 26 to 46% against H1N1pdm09, from 2 to 44% against H3N2 and from 50 to 85% against type B. For older adults, VE estimates ranged from 28 to 37% against H1N1pdm09, from 28 to 42% against H3N2 and from 58 to 66% against type B (11).

The moderate effectiveness in the elderly, in part due to the impact of immunosenescence (12), has necessitated the development of more immunogenic vaccine formulations in the form of high-dose vaccines, adjuvanted vaccines and recombinant vaccines. Studies have shown promising results for these enhanced vaccines. For instance, MF59-adjuvanted trivalent inactivated vaccines (MF59-TIV) have demonstrated higher effectiveness in preventing influenza-related hospitalizations and complications compared to non-adjuvanted vaccines in elderly populations (13). Immunosuppressed patients could also benefit from more immunogenic formulations. In an immunosuppressed population, high dose influenza vaccine was more immunogenic than standard dose influenza vaccine against A/H1N1 subtypes but not against H3N2 and B subtypes (14).

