9. RESEARCH METHODS

9.1 Study design

We will take advantage of the unique nationwide register-data available to us, and construct country-specific cohorts with individual-level information on dates of vaccination and dates of effectiveness endpoints together with relevant covariate information. All Nordic residents are assigned a unique personal identifier at birth or immigration, enabling linkage between register data. Nordic countries have universal and tax-financed healthcare systems and reporting to national registers is mandatory, providing near-complete follow-up of all residents over time.

The study period will start on 1st October 2024 in the three countries. This study start date corresponds to the start of the seasonal influenza vaccination program in the three countries. The study period will end on the last date of data availability at time of analyses during spring 2025.

The study design will build on our previous work with Covid-19 vaccination effectiveness in the Nordic countries (19,20). We will utilize a cohort design in a target trial emulation (TTE) framework to estimate both relative and absolute effects. The evaluations in 65+-yr-olds and risk groups 18-64-yr-olds will be designed as two separate target trial emulations. Key components of the specification and emulation of the pragmatic target trials of the effectiveness of brand-specific seasonal IVE using Nordic nationwide register data are included below in Table 1.

Table 1. Target trial emulation framework

Protocol	Target Trial Specification	Target Trial Emulation
Eligibility criteria	
 • Individuals 65+-years-of-age (trial 1) • Individuals in risk groups 18-64-yr-of-age (trial 2) • Have a permanent residency in Denmark, Finland, or Sweden at start of study period 	Same as for the target trials.
Treatment strategies	Vaccination with any of the following influenza vaccines InfluvacTetra, VaxigripTetra, FludTetra, FluarixTetra or Efluelda Tetra, October 1, 2024 to January 31, 2025 vs vaccination with placebo in the same period.	Same as for the target trials except vaccination with placebo is replaced by no vaccination with any of the vaccines under study.

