9.2 Setting

Within Denmark, Finland, and Sweden, we will include all individuals aged 65 years and above, and individuals below 65 years of age at high risk of adverse influenza outcomes, who are known residents. We will analyse each target group in separate cohorts in each country.

Eligibility criteria for study inclusion are:

- 1) Individuals 65+-years-of-age (trial 1)
- 2) Individuals in risk groups 18-64-yrs-of-age (trial 2)
- 3) Have a known residency within the specific country at start of study period

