9.8 Supplementary analyses and quality control

Confounding-by-indication and healthy vaccinee bias are critical methodological concerns in studies of influenza VE. (46). Confounding by indication would result in an underestimate of true effectiveness if individuals with comorbidities that increase the risk of the study outcome are more likely to get vaccinated. Healthy vaccinee bias occurs when healthy individuals are more likely to get vaccinated while the most frail and sick elderly with the highest risk of the study outcome are not vaccinated, especially at the end of life. In Table 8 below, we present the key possible confounders in studies of effectiveness and how they are likely to be associated with study exposures and outcomes.

Table 8. List of possible confounders in IVE studies

Possible Confounder	Influenza vaccination propensity	Influenza hospitalisation risk	All-Cause Mortality risk	Bias Direction for VE against	Bias direction for VE against

				influenza hospitalisation	all-cause mortality
Comorbidity	↑	↑	↑	Underestimate	Underestimate
High frailty	↓	↑	↑	Overestimate	Overestimate
Healthcare seeking	↑	↑	↓	Underestimate	Overestimate
Healthcare access	↑	↑	↓	Underestimate	Overestimate

The current state-of-the-art in observational vaccination effectiveness estimation is comprised mainly of two study approaches, the test-negative design and TTE. Both approaches seek to mitigate the impact of bias and confounding. Guilin and colleagues (47) evaluated the performance of the two approaches in the evaluation of Covid-19 VE estimation. In data with rich covariate information, they observed similar VE estimates from the two methods. In data with only a few covariates, the test-negative design tended to overestimate the VE, while the target trial emulation underestimated the VE.

To evaluate the potential for biases by healthcare-seeking behaviour or healthcare access, the TTE will be supplemented by a TND study. The TND study is only feasible in Denmark due to lack of test-negative results in Finland and Sweden. Moreover, supplementary analysis comprising of PERR, RDA, and Negative Control Outcomes Analyses will be conducted to allow for comparison and contextualisation of results. Moreover, to strengthen the robustness of findings, triangulation—integrating evidence from multiple analyses with different methodologies—can provide valuable insights into potential biases and enhance the interpretation of results.

Test-Negative Case Control design

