The test-negative case-control (TNCC) study design is a variant of the case-control method specifically developed for evaluating VE. (48) Due to unavailability of test negatives data in Finland and Sweden, we will conduct a TNCC study on Danish data only. In this approach, cases are individuals who test positive for influenza, while controls are those who test negative. The TNCC design offers several methodological strengths. It reduces bias from healthcare-seeking behaviour, as both cases and controls sought care and allows for efficient VE estimation during the influenza season. However, the TNCC design also has important limitations. It assumes that influenza vaccine does not affect the risk of other, non-influenza respiratory infections. (48) The design may be subject to bias if cases and

controls differ in disease severity. (49) Moreover, as the use of electronic healthcare records, including register-based data, for identifying cases and controls might cause bias (e.g., misclassification), and active enrolment of study participants is ideal in the TNCC design. (50) However, this increases the cost of the TNCC studies and limits its practicality to estimate VE against rare outcomes. Since a core assumption of the TNCC design is similar healthcare seeking behaviour among those who get tested, there is potential for selection bias if testing practices vary by vaccination status or other patient characteristics.

In the Danish population of individuals who were PCR-tested for influenza during the 2024–2025 season, we will employ a TNCC design to estimate the vaccine effectiveness against influenza infections during the 2024–2025 influenza season. We will exclude negative tests within 7 days of a previous negative test and within 21 days of a subsequent positive test. All tests within 90 days of a previous positive test will be excluded as these likely represent the same episode. Individuals can contribute with a maximum of one negative PCR test, which will be selected at random.

Patients will be considered vaccinated if they received an influenza vaccine at least 14 days before the PCR sample date. Patients will be considered unvaccinated if they have not received the influenza vaccine on the PCR test date or if they have received the influenza vaccine within two weeks before the PCR test date.

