Logistic regression models will be used to estimate the odds ratio (OR) with 95% CIs. Our main estimate of interest is the vaccine effectiveness defined by $(1-OR) \times 100\%$. The models will be adjusted for age, sex, region of residency and comorbidities. We will assess whether the frequency of testing differs between vaccinated and unvaccinated groups during the season, since differential testing could bias VE estimates. The testing frequency will be visualized in a plot stratified by month and vaccination status.

Prior event rate adjustment

A difference-in-differences approach in the form of prior event rate ratio (PERR) adjustment exists for evaluating healthy vaccinee bias for influenza outcomes. (51) The PERR method is built on the assumption that any differences in event rates unrelated to vaccination between vaccinated and unvaccinated individuals can be observed in the period before vaccination is available. This can be implemented using the pairwise version of PERR. (51)

The matching and censoring criteria from the main TTE analysis will be applied. As before, the day the seasonal vaccine dose was administered within each matched pair will serve as the index date for both individuals. For each individual within a matched pair, the pre-vaccination period will be the start of the 2024/2025 influenza season (1 October 2024) until the index date and the post-vaccination period will start on day 14 following the index date. We will identify individuals who ultimately receive a seasonal influenza vaccine (“future vaccinated”) and those who remain unvaccinated (“future unvaccinated”), evaluated at the end of the studied period or on the date of the outcome. Both groups will have the number of outcomes and the amount of person-time measured in the pre-vaccination period (to establish baseline event rates) and in the post-vaccination season (to assess post-vaccination event rates).

The outcome under study is influenza-related hospitalization. Given that influenza hospitalization may be less frequent at the start of the influenza season, we will assess whether sufficient events occur in the pre-vaccination period to produce stable estimates.

We will employ the pairwise version of PERR, which effectively compares the ratio of (current vs. pre-vaccinated) event rates in the vaccinated group to the ratio of (current vs. pre-vaccinated) event rates in the unvaccinated group. Formally:

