The study population will mirror the primary VE analysis, consisting of individuals aged 65 years or older, and adults under 65 years at high-risk. Vaccinated and unvaccinated individuals will be matched and the start of follow-up for matched pairs will be set at 14 days post-vaccination, ensuring alignment with the primary analysis. The statistical analysis will be conducted in the same way as our main cohort analysis, but negative control outcomes (lower back pain, clavicle fracture, and diverticulitis) will be evaluated instead of the influenza-related outcomes.

The results will be presented as cumulative incidence curves with RD and VE estimates. If no significant associations are found between influenza vaccination and the selected NCOs, this will support the validity of the primary VE analysis and suggest minimal residual confounding. If significant associations are observed, this will indicate residual confounding (e.g., differences in healthcare-seeking behavior) and warrant further exploration or caution in interpreting VE estimates.

Regression discontinuity analysis

For vaccination policies with treatment assignment according to age, regression discontinuity analyses (RDA) can be used to estimate a local average treatment effect (LATE) among individuals whose vaccination status is shifted by an eligibility threshold. Thus, we can estimate the LATE among 60-69-year-olds by comparing the risk in 65-69-yr-olds to the risk in the 60-64-yr-olds. This will provide a valid causal estimate under the assumptions of a) similar baseline risk of the influenza outcome in the two age groups, and b) strict adherence to the age recommendations. If adherence is not strict, we can

use fuzzy regression discontinuity analysis which uses an instrumental variables approach, where the cut-off is an instrument for actual treatment uptake. (52)

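### The Danish test-negative analysis is not tied to the two trial populations or to brand, so a gap between it and the cohort VE could not be cleanly attributed to healthcare-seeking bias

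*Protocol*

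**What the plan says.** Section 9.8 gives the TNCC a specific task: "To evaluate the potential for biases by healthcare-seeking behaviour or healthcare access, the TTE will be supplemented by a TND study". Only Denmark has negative test results, so the analysis is Danish.

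The source population is stated as "In the Danish population of individuals who were PCR-tested for influenza" during the 2024-2025 season. What follows are rules about tests: spacing between negatives, negatives shortly before a positive, repeat tests after a positive, and one negative per person. No age limit, risk-group limit or split by trial is given. On exposure: "Patients will be considered vaccinated if they received an influenza vaccine at least 14 days before the PCR sample date". On the model: "The models will be adjusted for age, sex, region of residency and comorbidities", with one main quantity of interest, (1-OR) x 100%. Brand does not appear.

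The cohort is built differently. Section 9.1: "The evaluations in 65+-yr-olds and risk groups 18-64-yr-olds will be designed as two separate target trial emulations". Section 9.2: "We will analyse each target group in separate cohorts in each country". Section 8 makes brand-specific VE the objective, and section 9.3 lists brand first among the stratifiers.

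Two other supplementary analyses in 9.8 are tied to that cohort. For negative control outcomes: "The study population will mirror the primary VE analysis, consisting of individuals aged 65 years or older, and adults under 65 years at high-risk". The prior event rate (PERR) analysis takes over the matching and censoring rules of the main emulation.

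**The concern.** A bias check by a second design works best when both designs estimate the same effect in the same people. Otherwise a gap has two possible explanations, bias in one design or a real difference in VE between the populations, and the data cannot separate them.

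The protocol gives reason to expect such a difference. Section 7 cites an evaluation in which "VE against any influenza was lower among patients with high-risk conditions (41%) than those without (48"%, with an interaction P of 0.02). Adjusting for age and comorbidity as main effects controls confounding by those factors. It does not remove effect modification: a single vaccine term averages the stratum-specific log odds ratios, with weights set by who was tested.

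Brand raises a similar issue. Table 3 gives Danish 65-69-year-olds InfluvacTetra or Vaxigrip Tetra and those aged 70+ Fluad Tetra. An any-vaccine odds ratio mixes these, while the cohort reports them one by one.

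At stake is the interpretation of the one supplementary analysis aimed most directly at healthcare seeking and access.

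**Working it through.** The protocol states no sample size or precision for the TNCC, so there is no figure to reproduce. The check has two parts.

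**1. Does the main-study population carry over?** Setting the parts of 9.8 side by side:

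| Analysis | Population as stated |
|---|---|
| Negative control outcomes | Mirrors the primary analysis |
| PERR | Main matching and censoring criteria |
| Regression discontinuity | Own population: ages 60-69, with high-risk people under 65 excluded |
| TNCC | Own population: Danes PCR-tested for influenza |

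The regression discontinuity row shows that section 9.2 eligibility does not pass automatically to every supplementary analysis, because its 60-64-year-olds belong to neither trial. The TNCC likewise names its own population. Inheritance is possible but not stated.

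**2. How far could population mix alone move the TNCC VE?** Take three strata: 65+, risk group 18-64, and everyone else.

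From the protocol:
- VE 41% (high-risk) and 48% (others), section 7.
- Danish coverage 75.6% (65+) and 29.2% (risk groups below 65), section 9.5.

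Assumed, because the protocol gives no figure:
- The 41% applies to both trials and the 48% to everyone else.
- Everyone else makes up 30-80% of test-negative controls, with coverage 5-20%.
- Target-group controls split 70:30 between 65+ and risk groups.
- Cases per control are 0.3, 0.3 and 0.6 in the three strata.

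The true odds ratio holds exactly in every stratum, so neither design is biased. In a stratum with n controls, coverage c and odds ratio OR = 1-VE, the controls are n(1-c) unvaccinated and nc vaccinated. Cases split in the ratio (1-c) : OR x c. The weight is w = 1/(sum of the reciprocals of the four counts), and the pooled log OR is approximately the w-weighted mean of the stratum log ORs.

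One cell, with everyone else at 60% of 100,000 controls and coverage 20%:
- Weights: 1,400 (65+), 461 (risk group), 2,652 (everyone else). Everyone else carries 2,652/4,513 = 0.588.
- ln(0.59) = -0.528 and ln(0.52) = -0.654.
- Pooled log OR = 0.412 x (-0.528) + 0.588 x (-0.654) = -0.602.
- Pooled VE = 1 - exp(-0.602) = 45.2%.

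A logistic model with a stratum term and one vaccine term, fitted to the expected counts, also gives 45.2%. Its results over the range:

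| Everyone else, share of controls | Coverage 5% | Coverage 20% |
|---|---|---|
| 30% | 41.7% | 43.1% |
| 60% | 43.0% | 45.2% |
| 80% | 44.7% | 46.6% |

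Against 41% in both trials, the shift is 0.7 to 5.6 points. With other assumed inputs (everyone else 30-70% of tests, coverage 8-25%; target coverage 70% and 29%; positivity 12%, 15% and 25%), inverse-variance weighting gives 42.0% to 46.1%, a shift of 1.0 to 5.1 points. If VE is 41% in every stratum, the model returns 41%: the shift needs effect modification.

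**Within the target groups.** Vaccinated Danes number about 1,211,000 x 0.756 = 915,516 (65+) and 554,780 x 0.292 = 161,996 (risk groups), or 85% and 15%. One odds ratio for both groups together would not be the VE of either trial if the two differ.

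**Brand.** Two brands with assumed VE of 30% and 50% pool to 1 - [s x 0.70 + (1-s) x 0.50], where s is the first brand's share. That is 44% at s = 0.3 and 36% at s = 0.7, matching neither brand.

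**The case against.** The strongest reply is that the TNCC text is silent rather than wrong. Section 9.2 and the abstract define the population for the whole study, section 9.3 lists brand as a stratifier without confining it to the cohort, and a SAP may add the restriction. This stands in part. A reader might infer that children and low-risk adults will certainly enter one logistic model. The protocol does not say that: it speaks of models in the plural, and inheritance cannot be excluded. What remains is that 9.8 does not leave the population open. It names one that differs from the cohort's, in a section that says so elsewhere when the main population applies.

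A reader might also infer that comparing the two designs says nothing about bias. That goes too far. Take the 700 Danish cases aged 65+ reported by 13 January 2025 (section 9.5), coverage 75.6%, VE 41% and an assumed positivity of 12%. This gives about 452 vaccinated and 248 unvaccinated cases, and 3,881 and 1,252 controls. The standard error of the log OR is sqrt(1/452 + 1/248 + 1/3,881 + 1/1,252) = 0.085, and the 95% interval for VE is about 30% to 50%. A shift of 1 to 5 points lies within that noise, so a large divergence would still be informative.

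Third, a reader might conclude that the TNCC is no check on any brand. Healthcare-seeking bias arises largely from the decision to be vaccinated, and section 9.3 says people receive whichever vaccine the site has. A pooled odds ratio therefore still informs on bias common to all brands. It just does not estimate a single brand's VE.

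Finally, the protocol has no rule that reads a TNCC-cohort gap as confounding. It speaks of triangulation and cautious interpretation. That limits the harm but does not make the comparison cleaner.

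**Conclusion.** The point holds in a limited form and is worth changing. As written, the TNCC is defined on everyone PCR-tested for influenza, with any influenza vaccine as exposure, and is tied neither to the two trials nor to brand. A difference from the cohort VE could then partly reflect population mix, by about 1 to 5 points, and could not be attributed cleanly to healthcare-seeking bias. The size rests on the cited 41% and 48% carrying over to these populations, and on assumed test shares, coverage outside the target groups, and positivity. The divergence is possible, not certain. The outcome is not at fault: infection in the TNCC corresponds to the cohort's primary laboratory-confirmed influenza outcome.

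**What to change.** In section 9.8, state that the main TNCC:

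- is restricted to people who meet trial 1 or trial 2 eligibility by the cohort's own definitions (age as 2024 minus birth year, residency and comorbidities at study start);
- is fitted separately in the two populations;
- gives brand-specific odds ratios for the main Danish brands where numbers allow;
- is compared with the Danish cohort estimate for laboratory-confirmed influenza, not with the pooled three-country estimate.

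An analysis of everyone tested can stay as a labelled secondary analysis.

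The cost is a short addition to the text, an eligibility filter, and separate trial and brand models in the Danish script. The statistical price is fewer tests and wider intervals, most of all in trial 2 and for less-used brands.

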9.3 Variables

Exposures

The Nordic countries conduct annual influenza vaccination campaigns that focus on specific population groups at high risk of severe outcomes from influenza. These groups generally include the elderly, individuals with chronic health conditions, pregnant women, children and healthcare workers (Table 2).

The vaccines are provided free of charge and are typically administered before the peak flu season. In Denmark, vaccines for season 2024/2025 are administered from October 1st, in Finland from September 30th and in Sweden from October 15th. In immunization programmes across the three Nordic countries, the most frequently used quadrivalent inactivated influenza vaccine brands have been InfluvacTetra, VaxigripTetra, FluadTetra, FluarixTetra, and Efluelda Tetra, which are formulated

according to WHO's recommendations. The vaccines contain both seasonal influenza A subtypes, A(H3N2) and A(H1N1) pdm09, and both influenza B lineages, B/Victoria and B/Yamagata. Overview of the country-specific vaccine brands, types and target populations is provided in Table 3. At vaccination at general practitioners, regional vaccination centres or workplaces, individuals are vaccinated with the influenza vaccine available at the location.

An individual is defined as vaccinated starting from and including the day of the first influenza vaccination during the ongoing season, and as unvaccinated if they have yet to receive a first vaccine in the ongoing season.

Table 2. Influenza Vaccination Recommendations in Nordic Countries for season 2024/2025

Country	Target Groups for Influenza Vaccination

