9.5 Study size

Below we describe key target group sizes, vaccination coverage and recorded influenza infection incidences in the three Nordic countries for the 2023-2024 season. This provides a good indication of the possible study size for the 2024-2025 season. We expect to include at least 3.2 million individuals who are included in the key target groups for seasonal influenza vaccination across the 3 Nordic countries.

In Denmark, the total population of individuals aged 65 years and older, along with the population at increased risk below 65 years of age, consisted of 1,211 million and 554,780 individuals, respectively, as of 20 December 2024. (39) From 1 October 2024 to 20 December 2024, influenza vaccination coverage in these target groups was 75.6% and 29.2%, respectively. (39) As of 13 January 2025, there were 700 confirmed cases of influenza, including 414 hospitalisations, in older adults above 65 years. (40)

In Finland, the total population of individuals aged 65 years and older was 1,315 million with a vaccine coverage of 61% during the 2023-2024 season. The population at increased risk aged between 18 and 64 years comprised of 0,52 million individuals. The influenza A incidence was 65.5 per 10,000 person-years, and influenza A hospitalisation incidence was 5.4 per 100,000 person-years. As of 20 January 2025, there were 3224 confirmed cases of influenza in the Finnish population, including 81 hospitalisations due to influenza in adults aged 65 years and above. (41,42)

In Sweden, the total population of elderly 65 years and above in the four regions under study comprise of 280,000 individuals, with national influenza vaccination coverage of 69% in the 2023/2024 season. (43)

We will utilize all available data to us from the countries' nationwide registers (Denmark and Finland), and regional data sources (Sweden). The statistical power of our proposed study will be reflected in the 95% CI of the effectiveness estimates. We expect to have robust statistical precision for the most widely used influenza vaccine brands within the current season. (44,45)

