9.7 Data analysis

Procedures

We will use a matched cohort design to evaluate the effectiveness of seasonal influenza vaccine in comparison with not receiving a seasonal influenza vaccine. Individuals who have received the vaccine will be matched on the day of vaccination with individuals who have not yet received the vaccine. Individuals will be matched on age (5-year bins), sex, region of residence, and selected comorbidities. The day the seasonal vaccine dose was administered within each matched pair will serve as the index date for both individuals. If individuals who were included as a matched non-vaccinated individual

(i.e., a reference individual) receive a vaccine later than the assigned index date, the pair will be right-censored on the day the non-vaccinated individual is vaccinated. In these cases, the non-vaccinated individuals will be allowed to potentially re-enter as vaccine recipients in a new matched pair on that given date.

Statistical analysis

We will follow individuals from day 14 after the index date (to ensure full immunisation) up until the day of an outcome event, death, emigration, or end of the study, whichever occurs first. Additionally, we will censor individuals with a positive PCR test for influenza in our follow-up period 14 and 30 days after the test (as a positive test will be part of the outcome definitions) for the influenza hospitalisation and death outcome analyses, respectively. We will right-censor matched pairs when the reference unvaccinated individual receives a vaccine during follow-up. Cumulative incidences will be estimated by the Aalen-Johansen estimator, and from these we will calculate the comparative VE as $1 - \text{risk ratio}$ at the start of week 18 (depending on data availability) since index date. The corresponding 95% CI will be calculated using the delta method. Country-specific estimates will be combined by random-effects meta-analyses implemented using the *mixmeta* package in R.

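### The Danish test-negative analysis counts people vaccinated in the previous two weeks as unvaccinated, unlike the cohort it is meant to check; any early protection then pulls its VE slightly towards zero

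*Protocol*

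**What the plan says.** The Protocol treats the first two weeks after vaccination in three ways.

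- **General exposure definition (Section 9.3).** "An individual is defined as vaccinated starting from and including the day of the first influenza vaccination during the ongoing season". A person is unvaccinated only until the first dose of the season.
- **Cohort (Section 9.7).** "We will follow individuals from day 14 after the index date (to ensure full immunisation". Days 0-13 are therefore outside follow-up for both members of a pair. Also, "We will right-censor matched pairs when the reference unvaccinated individual receives a vaccine during follow-up".
- **Test-negative analysis (Section 9.8, Denmark only).** "Patients will be considered vaccinated if they received an influenza vaccine at least 14 days before the PCR sample date". The unvaccinated are those with no vaccine by the test date, "or if they have received the influenza vaccine within two weeks before the PCR test date". VE is one minus the odds ratio from a logistic model.

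Section 9.8 also plans a sensitivity analysis that moves time zero to the day of vaccination, but only for the cohort design. Nothing in the Protocol excludes the two-week window from the test-negative analysis or tests its effect there.

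**The concern.** Section 9.8 adds the test-negative study to judge whether healthcare-seeking or access biases the cohort. That comparison is easiest to read when both designs use the same exposure contrast. Here they do not. The cohort compares people at least 14 days after vaccination with people not vaccinated. The test-negative analysis compares them with a mixture of unvaccinated people and people vaccinated days earlier. If the second group has some protection, influenza is less frequent in the reference group than in truly unvaccinated people, and VE is understated. Part of any gap between the two designs could then be read as healthcare-seeking bias when it comes from the definition.

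There is also a coding ambiguity that does not depend on bias: a test taken exactly 14 days after vaccination meets both the vaccinated and the unvaccinated wording.

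**Working it through.** The Protocol states no expected VE, sample size or share of recently vaccinated people for this analysis, so there is no planned figure to reproduce.

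**Inputs from the Protocol.** Section 9.5: "From 1 October 2024 to 20 December 2024, influenza vaccination coverage in these target groups was 75.6% and 29.2%, respectively" (65 years and older, and the risk group under 65, in Denmark). Window, reference group and effect measure: Section 9.8.

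**Assumptions, not in the Protocol.** True VE; relative risk RR in days 0-13 (protection e = 1 − RR); the uptake curve and the epidemic curve.

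**Formula.** Let s be the share of the reference group vaccinated in the last two weeks. Relative to truly unvaccinated people, the reference risk is 1 − s(1 − RR), so

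observed VE = 1 − (1 − VE) / [1 − s(1 − RR)].

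**Check 1: 65+, true VE 50%.** On a given day, s = [C(t) − C(t−14)] / [1 − C(t−14)], where C is coverage. With uptake ending at 75.6%, mean vaccination time 30-45 days after 1 October and an epidemic peak on 5 or 20 January, s weighted by cases is taken as 3-11%. This range depends on the shape assumed for both curves.

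| s | RR | Reference risk | Observed VE |
|---|---|---|---|
| 3% | 1.00 | 1.0000 | 50.0% |
| 11% | 1.00 | 1.0000 | 50.0% |
| 3% | 0.75 | 0.9925 | 1 − 0.5/0.9925 = 49.6% |
| 11% | 0.75 | 0.9725 | 1 − 0.5/0.9725 = 48.6% |
| 3% | 0.50 | 0.9850 | 1 − 0.5/0.9850 = 49.2% |
| 11% | 0.50 | 0.9450 | 1 − 0.5/0.9450 = 47.1% |

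RR 0.50 with a true VE of 50% means full protection from day 0. The loss runs from 0 to 2.9 points.

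**Check 2: day-by-day expected counts, true VE 40%.** Season of 152 days (1 October to 1 March), flat testing for non-influenza illness, linear uptake over 40 or 81 days.

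*Flat influenza incidence.* In 65+, recently vaccinated person-time is about 14 × 0.756/152 = 7.0%. With 40-day uptake, unvaccinated person-time is 1 − 0.756 × (152 − 20)/152 = 34.3%, so s is about 7.0/(7.0 + 34.3) = 17%. With 81-day uptake it is about 14%. Observed VE:

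- e = 0: 40.0%
- e = 20%: 37.9-38.3%
- e = 40% (full protection from day 0): 35.6-36.6%, a loss of up to 4.4 points
- e = −20% (raised early risk): 41.6-42.0%, so the sign reverses

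*Late-January peak with calendar time adjusted.* In 65+ the loss at e = 40% is 0.01 points (40-day uptake) to 1.0 point (81-day uptake).

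*Risk group under 65 (29.2% coverage), flat incidence.* s is 3.3-3.5% and the loss at e = 40% is 0.8-0.9 points. With a late-January peak and calendar time adjusted it is at most 0.14 points.

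**Boundary.** Vaccination on day d and a test on day d + 14 satisfies both definitions in Section 9.8, so two analysts could code it differently.

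**The case against.** Several counter-arguments have force.

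- **The direction is not given by the documents.** The Protocol reports no effectiveness for days 0-13; it says only that day 14 secures full immunisation. With no early protection there is no bias by this route, and with raised early risk the sign changes. This stands, and the point is stated conditionally.
- **A specific rule overrides a general one.** Section 9.3 is general and Section 9.8 is explicit, so an analyst would know what to do except on day 14. This is fair. The stronger argument is the mismatch with the cohort, not the wording of Section 9.3.
- **The designs differ anyway.** The test-negative analysis uses an odds ratio and tested people, the cohort a risk ratio at week 18, and the plan is triangulation. Negative control outcomes and testing frequency also address healthcare-seeking. This is true and limits the consequence, but it does not justify a further difference that is easily avoided.

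A reader might also infer more than the documents support.

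- **A much larger loss.** This needs a relative risk well below 0.5 in the window, or a share of 20% or more. With a true VE of 50%, a relative risk of 0.3 would make people in the first two weeks better protected (70%) than fully immunised people. Good health at vaccination is a weak explanation, because it should also lower testing for non-influenza illness and so largely cancel in the odds ratio. Shares of 20-30% arise only around early to mid-November under the assumed curves, when cases are few; they are not season-wide.
- **The calendar-time effect.** Section 9.8 states: "The models will be adjusted for age, sex, region of residency and comorbidities". Calendar time is not in that list. Without it and with a late-January peak, putting the window in the reference group lowers 65+ VE by a further 14 to 22 points in Check 2. But the estimate is already far off with the window excluded (−7.5% or −62.4% against a true 40%). That is a separate matter; it is not counted here and the fix below does not cure it.

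**Conclusion.** The concern holds in a limited form. The test-negative analysis places recently vaccinated people in its reference group, the cohort does not, and no planned analysis tests the difference. VE is pulled towards zero if there is any protection in days 0-13, and is unaffected by this route if there is none.

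For 65+ the loss is roughly 0-3 points at a true VE of 50%, given a 3-11% case-weighted share and a relative risk between 0.5 and 1. It reaches 4.4 points (true VE 40%) only with flat incidence from 1 October and full protection from day 0. Flat incidence fits poorly with the Protocol's own expectation of fewer influenza hospitalisations early in the season. In the risk group under 65 the loss is below 1 point. All of these sizes rest on assumed uptake and epidemic curves.

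A reader might infer that the main VE estimates are biased. They are not affected: this is a supplementary, Denmark-only analysis. What suffers is its use as a check, since a gap from the cohort cannot be attributed to healthcare-seeking alone. The point is modest in size but worth correcting before the analysis is run.

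**What to change.** In Section 9.8, under the test-negative design:

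1. Exclude tests sampled on days 0-13 after influenza vaccination.
2. Define unvaccinated as no influenza vaccine this season on or before the sample date.
3. Define vaccinated as influenza vaccination 14 days or more before the sample date.

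This gives the analysis the cohort's exposure contrast and removes the overlap on day 14.

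The cost is one sentence and one filter. Under flat testing and the stated coverage, about 14 × 0.756/152 = 7.0% of tests in 65+ and 14 × 0.292/152 = 2.7% in the risk group would be dropped. They fall mainly early in the season, when few cases are expected, so little information on VE is lost.
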